### 6.2.3. Duration of Response

Duration of Response (DoRi or DoRh [non-intensive only]) is defined, for patients from the FA set with a best overall response of CRi or better or CRh or better, as the time from first documentation of response (CRi or better or CRh or better) to the date of first documentation of objective disease relapse or death due to any cause. The censoring rules for DoRi/DoRh are discussed [Section 3.2.1](#).

$$\text{DoRi (months)} = [\text{date of event or censoring} - \text{first date of CRi or better} + 1] / 30.4375.$$

$$\text{DoRh (months)} = [\text{date of event or censoring} - \text{first date of CRh or better} + 1] / 30.4375.$$

Depending on the number of subjects who achieve a best overall response of CRi or better or CRh or better and subsequently have an event in each arm, Kaplan-Meier estimates (product-limit estimates) will be presented by treatment arm together with a summary of associated statistics including the median DoRi or DoRh (non-intensive only) time with two-sided 95% CIs. Inferential analyses (eg, a hazard ratio and p-value) will not be provided for duration of response.

Duration of response for the subset of patients with a best overall response of CR or better will also be analyzed.

An alternative definition of DoRi defined for all FA patients, may be explored for the intensive chemotherapy patients, where patients who have never achieved CRi or better will be considered having an event on Day 1.

#### **6.2.4. Time to Response (Non-intensive Only)**

Time to Response (TTRi or TTRh) is defined, for patients achieved CRi or better or CRh or better, as the time from the date of randomization to the first documentation of response (CRi or better or CRh or better).

The minimum, median, and maximum TTRi/TTRh for each treatment arm will be provided.

#### **6.2.5. Event-free Survival**

A 1-sided stratified log-rank test (stratified by ELN genetic risk, age [age  $\leq 60$  vs  $> 60$  years, and region [ROW vs China] for the intensive patients, and genetic risk and age  $< 75$  vs  $\geq 75$  years for the non-intensive patients]) will be used. Analyses will be performed using various EFS definitions as specified in [Section 3.2.1](#). Should over-stratification prevent model convergence or there exists a large imbalance in the distribution (eg, 90% or more subjects from one strata level), the intermediate and adverse ELN risk groups may be pooled in the analysis. EFS time associated with each treatment arm will be summarized using the Kaplan-Meier method and displayed graphically where appropriate. CIs for the 25th, 50th, and 75th percentiles of EFS probabilities will be reported (using Brookmeyer and Crowley method). In addition, the median EFS and its two-sided 95% CI using the same method will be provided for each stratum within each treatment arm separately. The Cox PH model will be fitted to compute the treatment HR and the corresponding 95% CI. The HR and its two-sided 95% CI will be provided for each stratum as well. The proportion of patients experiencing each type of EFS event (eg, TF, hematologic relapse, death) will also be summarized.

#### **6.2.6. Patient-Reported Outcomes**

All PRO analyses will be based on the FA **CCI** [REDACTED].

##### **6.2.6.1. MDASI-AML/MDS**

A MDASI-AML/MDS completion table will be constructed showing for each treatment group at each time point the number and percentage of subjects who completed and who had not completed the questionnaires, and also the reasons for non-completion.

Analysis of MDASI-AML/MDS will be based on the core cancer symptom score, the AML/MDS-specific symptoms score, the interference areas score, and also the 5 individual items of fatigue, disturbed sleep, dry mouth, muscle weakness, and lack of appetite. Note that Fatigue also appears in [Section 6.2.1](#) (as a key secondary endpoint) using a responder analysis.

A display of descriptive statistics including means, medians, standard deviations, and 95% confidence intervals at each assessment point will be provided. This will be done based on the observed values as well as on change from baseline values. Statistical comparison of the 2 treatment groups will be based on a longitudinal repeated measures mixed effects model using baseline as a covariate.

A graphical representation of observed mean and standard error over time and change from baseline over time by treatment arms will also be provided for the core cancer symptom score, the AML/MDS-specific symptom score, the interference area score, and also the 5 individual items of fatigue, disturbed sleep, dry mouth, muscle weakness, and lack of appetite.

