##### **Intensive Chemotherapy Study:**

- genetic risk (favorable vs intermediate vs adverse by ELN genetic risk categories) and age ( $\leq 60$  years vs  $> 60$  years).

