## 6. ANALYSES AND SUMMARIES

Analyses for the intensive and non-intensive chemotherapy studies will be conducted separately and independently. Unless otherwise stated, stratified analysis will be stratified based on ELN genetic risk, age  $\leq 60$  vs  $> 60$  years, and region (rest of world [ROW] vs China) for the intensive patients, and ELN genetic risk and age  $< 75$  vs  $\geq 75$  years for the non-intensive patients. The rate of stem cell transplantation is expected to be much lower for sites in China versus the ROW thus region is being added as a stratification factor for the intensive study analyses. The rate of stem cell transplantation is expected to be low in all regions in the non-intensive study.

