#### **6.2.6.2. EQ-5D-5L**

An EQ-5D completion table will be constructed showing for each treatment group at each time point the number and percentage of subjects who completed and who had not completed the questionnaires, and also the reasons for non-completion.

Analysis of EQ-5D-5L and EQ-VAS will follow similar methodology as for the MDASI endpoints described above. It will include a display of descriptive statistics including means, medians, standard deviations, and 95% confidence intervals at each assessment point. This will be done based on the observed values as well as on change from baseline values. Statistical comparison of the 2 treatment groups on EQ-5D and EQ-VAS will be carried out using a longitudinal repeated measures mixed effects model with baseline as a covariate.

In addition to the above analyses, a health status profile table showing the number of patients responding at each level on each dimension at each timepoint will also be constructed.

Finally as with the MDASI variables, a graphical representation of observed mean and standard error over time and change from baseline over time by treatment arms for EQ-5D and EQ-VAS will also be provided.

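### The MDASI and EQ-5D mixed models name only baseline as a covariate; adding the randomisation factors would calibrate their standard errors for three or four degrees of freedom

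*SAP*

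**What the plan says.** SAP 6.2.6.1 compares arms on the MDASI as follows: "Statistical comparison of the 2 treatment groups will be based on a longitudinal repeated measures mixed effects model using baseline as a covariate". The scores covered include "the core cancer symptom score, the AML/MDS-specific symptoms score, the interference areas score, and also the 5 individual items of fatigue". Four further single items complete the list: appetite loss, weak muscles, dry mouth and poor sleep. That makes three subscale scores and five items. SAP 6.2.6.2 compares EQ-5D and EQ-VAS "using a longitudinal repeated measures mixed effects model with baseline as a covariate". The patient-reported outcomes part of protocol 9.3.2 matches. None of the three places mentions ELN risk, age or region.

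SAP 3.4.1 lists the randomisation factors for the intensive study as "genetic risk (favorable vs intermediate vs adverse by ELN genetic risk categories) and age" (cut at 60 years). The non-intensive study uses the same two factors with the age cut at 75. Region is not listed there. It enters at the analysis stage, in the intensive study only, because transplant rates are expected to differ between China and elsewhere (SAP 6).

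SAP 6 has a general clause: "Unless otherwise stated, stratified analysis will be stratified based on ELN genetic risk", followed by age and, in the intensive study, region. It says which factors a stratified analysis uses. It does not say that the mixed models are stratified analyses.

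**The concern.** When allocation is balanced within strata that predict the outcome, the treatment estimate varies less than a model without those strata assumes. Such a model leaves the between-stratum variance in its error term, so it reports standard errors that are too large and tests that are conservative.

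Comparing patient-reported outcomes between arms is a stated secondary objective (SAP 2.1), so these models are meant for inference and not only for description. The contrast is clearest for the fatigue item. Its responder comparison in SAP 6.2.1 is stratified, while its mixed-model comparison in SAP 6.2.6.1 names only baseline. No reason is given for the difference.

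**Working it through.** **How the compared efficacy endpoints are tested**

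- OS (SAP 6.1): stratified log-rank test and stratified Cox model.
- EFS (SAP 6.2.5): stratified log-rank test; the Cox model is not stated to be stratified.
- Response rates (SAP 6.2.2, protocol 9.3.2): stratified CMH test and also an unstratified chi-square test.
- Fatigue responders (SAP 6.2.1): stratified CMH test.
- MDASI scores, EQ-5D and EQ-VAS (SAP 6.2.6.1, 6.2.6.2): mixed model, no stratification factor named.

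**Inputs.** The planned sizes are n = 400 (intensive) and n = 320 (non-intensive), from SAP 5.1.1. The main-effect terms are ELN risk (3 levels, 2 df) and age (1 df), plus region (1 df) in the intensive study. The added degrees of freedom are therefore k = 4 (intensive) and k = 3 (non-intensive). The plan gives no effect size, standard deviation or power for these models, so there is no planned figure to reproduce. R², the share of variance left after baseline that the added factors explain, is not in the documents and is assumed to lie between 0 and 0.10.

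**Change in standard error.** ANCOVA theory for a single comparison, used here as an approximation to the repeated-measures model, gives

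SE ratio = √[(1 − R²) × (1 + k/(n − k − 4))].

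For the intensive study the second factor is 1 + 4/392 = 1.0102. For the non-intensive study it is 1 + 3/313 = 1.0096. With one term per stratum cell in the intensive study (12 cells, k = 11) it is 1 + 11/385 = 1.0286. The power column takes 80% for the baseline-only model as an assumed reference.

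| Assumed R² | Intensive, k = 4 | Non-intensive, k = 3 | Intensive, 12 cells | Power from 80% (main effects) |
|---|---|---|---|---|
| 0 | 1.005 | 1.005 | 1.014 | 79.6% |
| 0.01 | 1.000 | 1.000 | 1.009 | 80.0% |
| 0.02 | 0.995 | 0.995 | 1.004 | 80.4% |
| 0.05 | 0.980 | 0.979 | 0.989 | 81.6% |
| 0.10 | 0.953 | 0.953 | 0.962 | 83.6% |

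Setting the ratio to 1 gives the break-even point, R² = k/(n − 4). It is 4/396 = 0.010 for main effects in the intensive study, 3/316 = 0.009 in the non-intensive study, and 11/396 = 0.028 for the 12 cells. If only 60% of intensive subjects contribute (n = 240, assumed), the main-effects range is 1.009 to 0.957.

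**Calibration of the baseline-only test.** With strata balanced by design, the baseline-only statistic has standard deviation √(1 − R²) under the null. Its two-sided type I error at nominal 5% is 2 × [1 − Φ(1.96/√(1 − R²))]:

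- R² = 0.02: 4.8%
- R² = 0.05: 4.4%
- R² = 0.10: 3.9%

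**Simulation check.** This used permuted blocks in six strata with 1,500 replicates per setting. At n = 400 and R² = 0.05:

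- The empirical standard deviation of the estimate was 0.0980 in one model and 0.0979 in the other, so the strata terms made almost no difference to it.
- The mean reported standard error was 0.1002 without the strata terms and 0.0977 with them.

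The ratio 0.0977/0.1002 = 0.975 agrees with √0.95 = 0.975. Under stratified allocation the penalty in the second factor of the formula is therefore smaller than the table allows. The reported standard error moves onto the true variability, while the variability itself hardly changes.

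**The case against.** The strongest reply is that little depends on this. The formal sequence is OS and then the fatigue responder test (SAP 5.1.2, 6.2.1), and that fatigue test is already stratified. The mixed models sit outside the sequence. Any error is in the safe direction, and a shift of -0.4 to +3.6 power points from an assumed 80% would not change the trial's conclusion. All of this stands, and it is why the point is minor.

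A reader might also infer stronger things that the documents do not support:

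- *That these are the only unstratified efficacy comparisons.* Response rates also get an unstratified chi-square test, and the EFS Cox model is not stated to be stratified. What holds is that each other compared efficacy endpoint has at least one stratified test.
- *That the sponsor decided to exclude the strata.* The model is described in one sentence, which does not spell out visit, interaction or covariance terms either, and nearby text is redacted. One can say only that baseline is the sole covariate named.
- *That the strata offer free precision.* R² is assumed, and below about 0.01 nothing is gained. Stratified allocation has already secured most of the real precision.
- *That the calibration argument covers region.* Region is not a randomisation factor, so the argument does not reach it.
- *That adding the strata makes missing-at-random more credible.* This is plausible, since the plan assumes different survival by age. But nothing in the documents shows that ELN risk or age predicts missing questionnaires once baseline is known.

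**Conclusion.** The point holds as a small, low-cost improvement. The MDASI and EQ-5D/EQ-VAS mixed models name only baseline, although two factors were built into the randomisation. If those factors predict the scores after baseline, the reported standard errors and confidence intervals are somewhat too wide. The tests remain valid and mildly conservative.

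For an assumed R² of 0 to 0.10, adding the factors changes the reported standard error by about +0.5% to -5%. The size rests on that assumed range, on full planned enrolment contributing data, and on the single-comparison approximation. It may be nil. The documents do not support calling the analysis invalid, or saying that a conclusion of the trial depends on it.

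**What to change.** In SAP 6.2.6.1 and 6.2.6.2, state the fixed effects of the mixed model: baseline score, treatment, visit, treatment-by-visit, and ELN risk and age group as recorded in the randomisation system. Enter ELN risk and age as main effects and not as one term per stratum cell, since the 12-cell version loses slightly at R² = 0.02. Apply the ELN pooling rule already in SAP 6.1 if levels are sparse. In the intensive study add region as well, for consistency with the plan's other stratified analyses.

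The cost is a short addition to each section and three degrees of freedom (non-intensive) or four (intensive). The variables are already collected. Protocol Section 9 lets the SAP modify the outlined methods and requires an amendment only for major changes to the primary endpoint definitions or their analyses, so a SAP revision should be enough.

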#### **6.2.6.2. EQ-5D-5L**

An EQ-5D completion table will be constructed showing for each treatment group at each time point the number and percentage of subjects who completed and who had not completed the questionnaires, and also the reasons for non-completion.

Analysis of EQ-5D-5L and EQ-VAS will follow similar methodology as for the MDASI endpoints described above. It will include a display of descriptive statistics including means, medians, standard deviations, and 95% confidence intervals at each assessment point. This will be done based on the observed values as well as on change from baseline values. Statistical comparison of the 2 treatment groups on EQ-5D and EQ-VAS will be carried out using a longitudinal repeated measures mixed effects model with baseline as a covariate.

In addition to the above analyses, a health status profile table showing the number of patients responding at each level on each dimension at each timepoint will also be constructed.

Finally as with the MDASI variables, a graphical representation of observed mean and standard error over time and change from baseline over time by treatment arms for EQ-5D and EQ-VAS will also be provided.

#### **6.2.6.3. PGIS**

PGIS will be used as an anchor for defining “responder” versus “non-responder” for MDASI-AML/MDS individual item Fatigue. Analysis method for anchoring is given in [Section 6.2.1](#) under analysis for Fatigue. A frequency distribution of PGIS categories at each time point by treatment arm will also be provided.

#### **6.2.6.4. PGIC**

As with PGIS, a frequency distribution of PGIC categories by treatment arm will be provided and PGIC will also serve as a secondary anchor to define a responder definition for MDASI-AML/MDS individual item Fatigue and as a sensitivity analysis for defining a “clinically important responder” on this endpoint.

CCI [REDACTED]

### 6.3. Other Endpoints

CCI [REDACTED]

[REDACTED]

[REDACTED]

[REDACTED]

[REDACTED]

[REDACTED]

[REDACTED]

CCI [REDACTED]

[REDACTED]

[REDACTED]

[REDACTED]

[REDACTED]

### 6.3.3. Pharmacokinetic Analysis

#### PK Parameters:

For intensive and non-intensive studies, the plasma trough concentration ( $C_{\text{trough}}$ ) will be reported. Descriptive statistics will be provided for these PK parameters in tabular form (n, mean, standard deviation (Stdev), CV, median, minimum, maximum, geometric mean and its associated CV) by cycle (or Induction 1, 2) and day.

#### PK Concentrations:

For drug concentrations, individual values and descriptive statistics (n, mean, Stdev, CV, median, minimum, maximum, geometric mean and its associated CV) will be presented by cycle (or Induction 1, 2), day of assessment, and nominal time in tabular form.

### 6.3.4. Population Pharmacokinetic Analysis or PK/PDx Modeling

PK and pharmacodynamics (PDx) data from this study may be analyzed using modeling approaches and may also be pooled with data from other studies to investigate any causal relationship between study treatment exposure and biomarkers or significant safety endpoints. The results of these analyses, if performed, may be reported separately.

CCI [REDACTED]

[REDACTED]

[REDACTED]

- | [REDACTED]
- | [REDACTED]
- | [REDACTED]
- | [REDACTED]
- | [REDACTED]
- | [REDACTED]
- | [REDACTED]
- | [REDACTED]
- | [REDACTED]
- | [REDACTED]
- | [REDACTED]
- | [REDACTED]
- | [REDACTED]
- | [REDACTED]
- | [REDACTED]
- | [REDACTED]

[REDACTED]

CCI

## **6.5. Baseline and Other Summaries and Analyses**

### **6.5.1. Baseline Summaries**

The following analyses will be based on the FA set overall and separately by treatment arm.

Descriptive baseline summaries by race will not be performed for the China subset.

- **Demographic and Physical Characteristics**

The following demographic and baseline characteristics will be summarized by number and percentage:

- Gender (male, female).
- Age (18-<45; 45- <65; 65-<75;  $\geq 75$ ), additionally  $\leq 60$  years vs  $> 60$  years for intensive patients and  $< 75$  years vs  $\geq 75$  years for non-intensive patients.
- Race (White, Black, Asian, Other), Racial designation for Asian (Japanese, Korean, Chinese, other), ethnicity (Hispanic/Latino, non-Hispanic/Latino).
- Eastern Cooperative Oncology Group (ECOG) Performance status.

Age (continuous), height (cm), weight (kg), will be summarized with descriptive statistics (mean, median, standard deviation, minimum, and maximum).

- **Disease Characteristics**

The following baseline disease characteristics will be summarized by number and percentage:

- ELN risk category at randomization.
- Reasons for choosing non-intensive study.
- Bone marrow blasts (<30, ≥30%).
- White blood cell (WBC) count (<10, ≥10x10^9/L).
- Platelet count (<50, ≥50x10^9/L).
- Hemoglobin (<100, ≥100 g/L).
- Genetic Abnormality (eg, NPM1 MUTATION WITHOUT FLT3-ITD, etc).
- Hematological Disease History (de novo, secondary).

Time from initial diagnosis to screening, peripheral blood blasts and bone marrow blasts (%), WBC (10^9/L), platelet count (10^9/L), and hemoglobin (g/L) will be summarized with descriptive statistics (mean, median, standard deviation, minimum, and maximum).

- **Stratification Factors**

The number of patients per strata will be summarized based on strata reported in the randomization system as well as on the CRF including a summary of any discordance. The following categories will be considered:

**Intensive Chemotherapy Study**

- age ≤60 years, favorable ELN risk category, and ROW.
- age ≤60 years, intermediate ELN risk category, and ROW.
- age ≤60 years, adverse ELN risk category, and ROW.
- age >60 years, favorable ELN risk category, and ROW.
- age >60 years, intermediate ELN risk category, and ROW.
- age >60 years, adverse ELN risk category, and ROW.
- age ≤60 years, favorable ELN risk category, and Chinese site.

- age  $\leq 60$  years, intermediate ELN risk category, and Chinese site.
- age  $\leq 60$  years, adverse ELN risk category, and Chinese site.
- age  $> 60$  years, favorable ELN risk category, and Chinese site.
- age  $> 60$  years, intermediate ELN risk category, and Chinese site.
- age  $> 60$  years, adverse ELN risk category, and Chinese site.

### **Non-intensive Chemotherapy Study**

- age  $< 75$  years and favorable ELN risk category.
  - age  $< 75$  years and intermediate ELN risk category.
  - age  $< 75$  years and adverse ELN risk category.
  - age  $\geq 75$  years and favorable ELN risk category.
  - age  $\geq 75$  years and intermediate ELN risk category.
  - age  $\geq 75$  years and adverse ELN risk category.
- **Medical History**
    - Medical history will be coded using the most current version of MedDRA and summarized by MedDRA's System Organ Class (SOC) and PT. Each patient will be counted only once within each PT or SOC. Summaries will be ordered by primary SOC and PT in descending order of frequency by the experimental treatment arm. Separate summaries will be provided for past and present conditions.

### **6.5.2. Study Conduct and Patient Disposition**

The following analyses will be based on the FA set overall and separately by treatment arm.

#### **6.5.2.1. Patient Disposition**

A summary of the number of patients screened and enrolled overall and by country and site will be provided.

Discontinuation of treatment overall and for each study drug, discontinuation of post-treatment follow-up, and discontinuation of study will be summarized separately and by reason for discontinuation. Discontinuations from study treatment and post-treatment follow-up will be summarized using the safety analysis set and discontinuations from the study will be summarized using the FA set. Once a patient discontinues all study drugs they will be considered discontinued overall from study treatment. The reason and date corresponding to the last drug discontinued should be used for the overall summary. If

multiple drugs were discontinued on the same date with different reasons then the reason for discontinuing blinded therapy will be used.

Patients completing blinded therapy will be identified as either those who were confirmed MRD negative and were treated for less than 2 years or those who were treated for 2 years.

Discontinuations from study treatment due to adverse events will be identified as either related or not related to study treatment. If causality is missing the event will be considered related to treatment. If multiple events lead to study treatment discontinuation and at least one was considered related, discontinuation will be reported as related to study treatment.

An additional summary to meet European Union Disclosure requirements will categorize discontinuations due to adverse events based on the following categories:

- Adverse Event, not serious.
- Adverse event, serious non-fatal.
- Adverse event, serious fatal.

